7.4.1 Type I Error Control for Key Secondary Endpoints

There are four planned comparisons among the two key secondary efficacy endpoints. These comparisons are defined based on pooled data from Study OPN-FLU-CS-3205 and Study OPN-FLU-CS-3206. Testing will continue based on closed testing procedure with $\alpha=0.05$, if both primary hypotheses are met, as follows:

1. OPN-375 372 μ g versus placebo in change from baseline to Week 4 in CSNS in subjects who were symptomatic at trial entry despite reported use of an intranasal steroid for treatment of CRS within 30 days of Visit 1
2. OPN-375 186 μ g versus placebo in change from baseline to Week 4 in CSNS in subjects who were symptomatic at trial entry despite reported use of an intranasal steroid for treatment of CRS within 30 days of Visit 1
3. OPN-375 372 μ g versus placebo in the frequency of acute exacerbations of CRS over 24 weeks
4. OPN-375 186 μ g versus placebo in the frequency of acute exacerbations of CRS over 24 weeks

7.5 Estimation - Other Secondary Efficacy Endpoints

All statistical analyses in this section that reference the primary MMRM and ANCOVA models described in Section 7.1.5 will include the same factors as their respective primary models, except for the baseline covariate. The baseline covariate for the specific endpoint described in this section will be used, unless otherwise specified.

In addition, a combined dose group (OPN-375 186 μ g, OPN-375 372 μ g) is defined in all models of primary and secondary endpoints by including appropriate contrasts, assigning equal weight to each dose, to obtain the inferential statistics for combined doses and for the comparison: combined doses versus placebo.

Intercurrent events for secondary endpoints will be addressed as described in Section 7.1.3 for the primary estimand, unless otherwise indicated. For the treatment policy estimand, (reference Section 7.1.3, criteria 3,c), missing data due to study discontinuation will be handled as described in Section 7.1.5 for the primary MMRM and ANCOVA models, respectively. Further details on the MI method for endpoints based on the ANCOVA model are described in Section 10.

7.5.1 Averages of Daily Nasal Symptom Diary – Individual & CSNS

Details on the daily nasal symptoms diary and the derivation of the CSNS is provided in Section 9.3.1. For the 7-day averages of AM, PM, and instantaneous, reflective individual nasal symptoms scores, the worst score of '3' will be applied to the individual symptom scores for the composite strategy, per the primary estimand. For the 7-day average of AM, PM, and instantaneous, reflective CSNS scores, the worst score of '9' will be applied; further details regarding the assignment of a worst score to the diary data are provided in Section 9.3.1. The 7-day windows used to define the 7-day averages from baseline through Day 84 (Week 12) are provided in Section 9.1.2.1, Table 9.1.

The following individual and CSNS endpoints will be analyzed:

- Changes from baseline to Weeks 4, 8 and 12 in the 7-day average of AM, PM, and instantaneous, reflective individual nasal symptoms scores (16 endpoints at each time point: four individual nasal symptom scores each at four endpoints).
- Changes from baseline to Weeks 4, 8 and 12 in the 7-day average of AM, PM, and instantaneous, reflective CSNS scores (4 endpoints at each time point).

These endpoints will be analyzed using the MMRM model described in Section 7.1.5 with the repeated measures including Week 4, 8, 12. The model-based LS mean difference between each active treatment group and placebo (active-placebo), 95% CI, and nominal p-value will be displayed for each analysis time point.

7.5.2 SNOT-22 Total Score and Domain Scores

The SNOT-22 instrument is described in Section 9.3.3. For SNOT-22 total score, a poor score is defined as follows: for a subject with a baseline SNOT-22 total score ≥ 92 , a value of '110' is assigned; if baseline SNOT-22 total score < 92 , a poor score is defined as baseline SNOT-22 total score + 18 for the composite strategy, per the primary estimand. For the individual Domain SNOT-22 scores, the worst value for the respective domain (Table 9.4) will be applied.

Changes from baseline to Weeks 4, 8, 12 and 24/ET in SNOT-22 total scores and each of the 5 Domain scores will be analyzed using the MMRM model described in Section 7.1.5 where the repeated measures include change from baseline in SNOT-22 total scores at Week 4, 8, 12, and 24/ET. The model-based LS mean difference between each active treatment group and placebo (active-placebo), 95% CI, and nominal p-value will be displayed for each analysis time point.

7.5.2.1 SNOT-22 in Subjects on INS at Baseline – Pooled Analysis

The following analysis is defined by pooling the data from Study OPN-FLU-CS-3205 and Study OPN-FLU-CS-3206. Change from baseline to Week 24/ET in SNOT-22 total score in subjects who report using an intranasal, topically acting nasal steroid (INS) for the treatment of CRS within 30 days of Visit 1 will be analyzed using the same MMRM model described above, and the model will include a categorical effect term for protocol (CS-3205, CS-3206).

7.5.3 Percentage of Opacified Volume

Percentage of opacified volume, and average (APOV) and worst POV (WPOV) are defined in Section 9.3.2. For APOV-E, APOV-M, WPOV, WPOV-E, WPOV-M the following endpoints are analyzed.

7.5.3.1 Average Percentage of Opacified Volume in the Individual Sinuses

Change from baseline in APOV-E and APOV-M will be analyzed with the ANCOVA model described in Section 7.1.5. A poor score is assigned as defined in Section 7.1.3 for the APOV co-primary endpoint. The model-based LS mean difference between each active treatment group and placebo (active-placebo), 95% CI, and nominal p-value will be displayed.

7.5.3.2 Percentage of Opacified Volume (POV) in the Worst Sinus

- i. Change from baseline to Week 24/ET in the WPOV sinus at baseline.

For WPOV, a poor score is defined as follows: for a subject with a baseline WPOV $\geq 71\%$, a value of '100%' is assigned; if baseline WPOV $< 71\%$, a poor score is defined as baseline WPOV + 29%.

- ii. Change from baseline to Week 24/ET in the WPOV-E sinus at baseline.

For WPOV-E, a poor score is defined as follows: for a subject with a baseline WPOV-E $\geq 67\%$, a value of '100%' is assigned; if baseline WPOV-E $< 67\%$, a poor score is defined as baseline WPOV-E + 33%.

- iii. Change from baseline to Week 24/ET in the WPOV-M sinus at baseline.

For WPOV-M, a poor score is defined as follows: for a subject with a baseline WPOV-M $\geq 69\%$, a value of '100%' is assigned; if baseline WPOV-M $< 69\%$, a poor score is defined as baseline WPOV-M + 31%.

Changes from baseline to Week 24/ET for (i) WPOV (ii) WPOV-E, and (iii) WPOV-M will be analyzed with the ANCOVA model described in Section 7.1.5. The model-based LS mean difference between each active treatment group and placebo (active-placebo), 95% CI, and nominal p-value will be displayed.

7.5.4 Qualitative CT Scan Assessment

The protocol for qualitative CT scan imaging assessments is based on the Image Review Charter (IRC) – Revision C, (29 January 2020). Qualitative CT scan assessments will be performed at baseline and Week 24/ET in accordance with the IRC for Lund-Mackay Staging (LM) and Zinreich Modification of the Lund-Mackay Staging (ZLM). Further detail on LM and ZLM image scoring metrics and adjudication procedure, and the definitions of the analysis variables derived from these scoring metrics is provided in Section 9.3.6.

For LM total score, a poor score is defined as follows: for a subject with a baseline LM total score ≥ 18 , a value of '24' is assigned; if baseline LM total score < 18 , a poor score is defined as baseline LM total score + 6 for the composite strategy, per the primary estimand.

For ZLM total score, a poor score is defined as follows: for a subject with a baseline ZLM total score ≥ 39 , a value of '50' is assigned; if baseline ZLM total score < 39 , a poor score is defined as baseline ZLM total score + 11 for the composite strategy, per the primary estimand.

Other LM and ZLM efficacy endpoints will be assigned scores for the composite strategy, per the primary estimand, as listed in Table 7.1.

Table 7.1
Worst Score Assignment for LM and ZLM efficacy variables

Efficacy Variable	LM worst score	ZLM worst score
Ethmoid + Maxillary	12	30
Sinus Pair	4	10

7.5.4.1 Lund-Mackay (LM) Staging

Changes from baseline to Week 24/ET in the LM Total Score, LM scores for ethmoids and maxillary sinuses combined, and the LM score for each sinus pair will be analyzed using the ANCOVA model described in Section 7.1.5. The model-based LS mean difference between each active treatment group and placebo (active-placebo), 95% CI, and nominal p-value will be displayed.

A sensitivity analysis of reviewer agreement will be provided as a ‘3X3’ cross-classification table of Reviewer 1 versus Reviewer 2 assigned LM scores.

7.5.4.2 Zinreich Modification of the Lund-Mackay Staging (ZLM)

Changes from baseline to Week 24/ET in the ZLM Total Score, ZLM scores for ethmoid (L, R) and maxillary (L, R) sinuses combined, the ZLM score for each sinus pair (ethmoid, maxillary) and the ZLM score for the worst sinus among maxillary (L, R) and ethmoid (L, R) sinuses (WZLM) will be analyzed using the ANCOVA model described in Section 7.1.5. The model-based LS mean difference between each active treatment group and placebo (active-placebo), 95% CI, and nominal p-value will be displayed.

A sensitivity analysis of reviewer agreement will be provided as a ‘6X6’ cross-classification table of Reviewer 1 versus Reviewer 2 assigned ZLM scores.

7.5.5 PSQI Global and Component Scores

The Pittsburgh Sleep Quality Index (PSQI) is a validated, self-rated questionnaire, which assesses sleep quality and disturbances over a 1-month time interval; further details on the PSQI instrument are provided in Section 9.3.7. PSQI is measured at baseline, Week 12, and Week 24/ET. For PSQI Global score, a poor score is defined as follows: for a subject with a baseline PSQI Global score ≥ 17 , a value of ‘21’ is assigned; if baseline PSQI Global score < 17 , a poor score is defined as baseline PSQI Global score + 4 for the composite strategy, per the primary estimand. For PSQI component scores, the worst score for the component will be assigned.

Changes from baseline to Week 12 and Week 24/ET in PSQI Global score and component scores (reference Appendix, Section 13.1) will be analyzed using the MMRM model described in Section 7.1.5, where the repeated measures include change from baseline scores at Week 12 and 24/ET. The model-based LS mean difference between each active treatment group and placebo (active-placebo), 95% CI, and nominal p-value will be displayed for each analysis time point.

7.5.5.1 PSQI Global Score – Pooled Analysis

This analysis is defined by pooling the data from Study OPN-FLU-CS-3205 and Study OPN-FLU-CS-3206.

Change from baseline to Week 24/ET in PSQI Global score will be analyzed using the MMRM model described above and the model will include a categorical effect term for protocol (CS-3205, CS-3206).

7.5.6 SF36v2 – MCS and PCS Domains

The SF36v2 instrument is described in Section 9.3.4. For SF36v2 MCS domain score, a poor score is defined as follows: for a subject with a baseline MCS Domain score ≤ 18 , a value of ‘0’ is assigned; if baseline MCS Domain score > 18 , a poor score is defined as baseline MCS Domain score –18 for the composite strategy, per the primary estimand.

For SF36v2 PCS domain score, a poor score is defined as follows: for a subject with a baseline PCS Domain score ≤ 11 , a value of ‘0’ is assigned; if baseline PCS Domain score > 11 , a poor score is defined as baseline PCS Domain score –11 for the composite strategy, per the primary estimand.

The change from baseline to Week 24/ET in SF-36v2 PCS and MCS t-scores, respectively, will be analyzed using the ANCOVA model described in Section 7.1.5. The model-based LS mean difference between each active treatment group and placebo (active-placebo), 95% CI, and nominal p-value will be displayed.

7.5.7 SF36v2 – Individual Health Domains

The SF36v2 instrument is described in Section 9.3.4. For SF36v2 Individual Health Domain scores, the worst SF36v2 Individual Health Domain score of ‘0’ will be assigned for the composite strategy, per the primary estimand.

The change from baseline to Week 24/ET in SF-36v2 Health Domain scores will be analyzed using the ANCOVA model described in Section 7.1.5. The model-based LS mean difference between each active treatment group and placebo (active-placebo), 95% CI, and nominal p-value will be displayed.

7.5.8 PGIC - “Subject” Global Impression of Change

PGIC and endpoints “Improved” and “Much Improved” are defined in Section 9.3.8. PGIC is measured at Weeks 4 and 24/ET. For PGIC endpoints, the worst score of “Not Improved” will be assigned for each endpoint (Table 9.6) for the composite strategy, per the primary estimand.

The proportion of subjects “Improved” or “Much Improved” will be compared between treatments (each active versus placebo) based on a logistic regression MMRM using the generalized linear mixed model (GLMM). The logistic regression MMRM model will include categorical effects for previous sinus surgery (Y,N), nasal polyp status (present, absent), treatment (OPN-375 186 µg, OPN-375 372 µg, placebo), week (4, 24/ET) and treatment-by-week interaction,. Treatment group comparisons will be estimated from the least squares mean difference between treatments from treatment-by-visit interaction and will be presented as odds ratios with accompanying p-

values and 95% confidence intervals. The model-based LS Mean estimate of the percentage response in each treatment group will also be presented.

Model parameters will be estimated using restricted pseudo-likelihood with Newton-Raphson ridging optimization and the Kenward-Roger method for calculating the denominator degrees of freedom. An unstructured covariance matrix will be used to estimate within-subject error. The logistic regression MMRM will be implemented in SAS PROC GLIMMIX.

7.5.9 QIDS-SR Total Score and Severity of Depression Categories

The QIDS-SR Total Score and Severity of Depression categories are described in Section 9.3.9. For QIDS-SR total score, a poor score is defined as follows: for a subject with a baseline QIDS-SR total score ≥ 22 , a value of '27' is assigned; if baseline QIDS-SR total score < 22 , a poor score is defined as baseline QIDS-SR total score + 5 for the composite strategy, per the primary estimand.

Change from baseline to Week 24/ET for QIDS-SR total scores will be analyzed using the ANCOVA model described in Section 7.1.5. The model-based LS mean difference between each active treatment group and placebo (active-placebo), 95% CI, and nominal p-value will be displayed.

The proportion of subjects reporting "None" or "Mild" depression (Table 9.7) will be compared between treatments (each active versus placebo) based on a logistic regression at Week 24/ET. The logistic model will include categorical effects for previous sinus surgery (Y, N), nasal polyp status (present, absent), treatment (OPN-375 186 μ g, OPN-375 372 μ g, placebo), and baseline QIDS-SR total score. Model-based odds ratios between each active treatment group and placebo (active-placebo), 95% CI, and nominal p-value will be displayed.

The statistical analyses of the proportion of subjects reporting "None" or "Mild" depression will include all subjects with a baseline and Week 24/ET QIDS-SR total score; no imputation of QIDS-SR depression categories will be performed.

7.5.10 Time to First CRS Exacerbation Event

How an acute CRS exacerbation is defined and captured in this study, as well as the definition of time to first acute CRS exacerbation is described in Section 9.3.5. The analyses of the frequency of acute CRS exacerbation events is described in Section 7.3.2

Subjects who complete the study without an acute CRS event will be censored at Week 24/ET. Regarding intercurrent events, use of systemic corticosteroids is included in the definition of acute exacerbation; subjects who have surgery or study discontinuation events will be censored at the time of the intercurrent event. Subjects who discontinue treatment are followed to study completion or intercurrent event as described in Section 7.1.3.

The Kaplan-Meier method will be used to estimate the time to first acute CRS exacerbation event, and the median, 25th and 75th percentiles of time to first acute CRS exacerbation events (in weeks). A figure for Kaplan-Meier estimates by treatment group and 95% CI for the median time (in weeks) will be presented.

The stratified log-rank test will be used to compare the time to first acute CRS exacerbation event between each active treatment group and placebo including stratification factors sinus surgery

status (Y vs N) and nasal polyp status (present vs absent) at baseline. The nominal p-value from the stratified log-rank test will be presented.

7.5.11 SIT Scores

The Smell Identification Test (SIT) is described in Section 9.3.10. The SIT is administered at baseline and Week 24/ET. The SIT score represents the number of correct answers to the 40 response items. For SIT scores, a worst score of '10' will be assigned, per the primary estimand. A SIT score of '10' is the expected number of correct responses due to chance alone; i.e., a SIT score of '10' is consistent with total anosmia.

Change from baseline to Week 24/ET in SIT scores will be analyzed using the ANCOVA model described in Section 7.1.5. The model-based LS mean difference between each active treatment group and placebo (active-placebo), 95% CI, and nominal p-value will be displayed.

7.6 Health Economic Outcomes Research (HEOR) Endpoints

7.6.1 Surgical Intervention Assessment (SIA)

The surgical intervention assessment (SIA) is performed at baseline and Week 24/ET. This assessment includes a question to the subject as well as an objective assessment.

For the question, subjects are asked, "If symptoms of CRS were to continue at the current severity level would subject consider undergoing sinus surgery if it were recommended to subject today by subject's physician?"

The Surgical Intervention Assessment (SIA) is based on the following pre-defined, objective criteria used to create a standardized determination of whether or not a subject is eligible for sinus surgery.

a) Subjects **with** polyps present at baseline will have to have all of the following:

- used a topical intranasal corticosteroid (≥ 8 weeks duration)
- used a short-course of systemic corticosteroid (1- to 3-week duration)
- SNOT-22 total score ≥ 20
- Lund-Mackay CT score ≥ 1

b) Subjects **without** polyps present at baseline will have to have all of the following:

- used topical intranasal corticosteroid (≥ 8 weeks duration)
- used either a short course of broad-spectrum/culture-directed systemic antibiotic (2 to 3 weeks duration) or a prolonged course of systemic low-dose anti-inflammatory antibiotic (i.e., macrolide or trimethoprim/sulfamethoxazole) (≥ 12 weeks duration)
- SNOT-22 total score ≥ 20
- Lund-Mackay CT score ≥ 1

A subject who satisfies the criteria in either (a) or (b) above is defined to have the event: eligible for sinus surgery. Only subjects who have SIA completed at both baseline and Week 24/ET will be included in the analysis.

The number and percentage of subjects answering Yes/No to the surgery question, and the number and percentage of subjects who are eligible for surgery (Yes/No) based on SIA within each active treatment group and placebo will be summarized in a '2x2' contingency table representing baseline versus Week 24/ET. McNemar's test will be used to assess the extent to which subjects improve ('Yes' at baseline to 'No' at Week 24/ET) versus worsen ('No' at baseline versus 'Yes' at Week 24/ET) within each treatment group, and the odds ratio (improved versus worsened) and 95% confidence interval will be presented for each treatment group.

The proportion of subjects who meet the SIA eligibility criteria for surgery at Week 24/ET will be compared between treatments with a logistic regression model including categorical effects for previous sinus surgery (Y, N), nasal polyp status (present, absent), treatment (OPN-375 186 µg, OPN-375 372 µg, placebo), and baseline SIA eligibility (Yes, No) as a covariate. Treatment group comparisons will be estimated from the least squares mean difference between treatments and will be presented as odds ratios with accompanying p-values and 95% confidence intervals.

The same logistic model will be used for the proportion of subjects answering 'yes' to the surgery question at week 24/ET, with baseline response as a covariate.

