## 4 SELECTION AND WITHDRAWAL OF SUBJECTS

### 4.1 Inclusion Criteria

Potential subjects must meet the following criteria to enter this study:

1. men or women aged 18 years and older at baseline visit
2. women of child bearing potential must be abstinent, or if sexually active:
  - a. be practicing an effective method of birth control (eg, prescription oral contraceptives, contraceptive injections, contraceptive patch, intrauterine device, double-barrier method [eg, condoms, diaphragm, or cervical cap with spermicidal foam, cream, or gel], or male partner sterilization) before entry and throughout the study, or
  - b. be surgically sterile (have had a hysterectomy or bilateral oophorectomy, tubal ligation, or otherwise be incapable of pregnancy), or
  - c. be postmenopausal (amenorrhea for at least 1 year).
3. women of child-bearing potential must have a negative urine pregnancy test at Visit 1 (Screening)
4. must have a history of CRS and be currently experiencing 2 or more of the following symptoms, one of which has to be either nasal congestion or nasal discharge (anterior and/or posterior nasal discharge) for equal to or greater than 12 weeks:
  - nasal congestion
  - nasal discharge (anterior and/or posterior nasal discharge)
  - facial pain or pressure
  - reduction or loss of smell
5. endoscopic evidence of nasal mucosal disease, with edema, purulent discharge, or polyps in middle meatus, bilaterally, or presence of bilateral disease on a prior CT scan performed within 14 days of Visit 1
6. must have confirmatory evidence via CT of bilateral sinus disease (have at least 1 sinus on each side of nose with a Lund-Mackay score of  $\geq 1$ )
7. baseline CT scan must show a combined  $\geq 25\%$  opacification of the ethmoid sinuses and  $\geq 25\%$  opacification of at least 1 maxillary sinus
8. must have at least moderate symptoms (as defined in [Section 7.2](#)) of nasal congestion as reported by the subject, on average, for the 7-day period preceding Visit 1 (Screening) run-in
9. must have an average morning score of at least 1.5 for congestion on the Nasal Symptom Scale (as defined in [Section 7.2](#)) recorded on the subject diary over a 7-day period during the first 14 days of the single-blind run-in period
10. must demonstrate an ability to correctly complete the daily diary during the run-in period to be eligible for randomization

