### 9.6 Other Secondary Efficacy Analyses

All statistical analyses in this section that reference the primary MMRM and ANCOVA models described in Section 9.3.4 will include the same factors as their respective primary models, except for the baseline covariate. The baseline covariate for the specific endpoint will be used, unless otherwise specified.

In addition, a combined dose group (OPN-375 186  $\mu$ g, OPN-375 372  $\mu$ g) is defined in all models of primary and secondary endpoints by including appropriate model contrasts, assigning equal weight to each dose, to obtain the inferential statistics for combined doses, and for the comparison: combined dose versus placebo.

Intercurrent events for secondary endpoints will be addressed as described in Section 9.3.3 for the primary estimand, unless otherwise indicated, and poor scores assigned to secondary endpoints are defined in the SAP. For the treatment policy estimand, missing data due to study discontinuation will be handled as described in Section 9.3.4 for the primary MMRM and ANCOVA models, respectively.

The following secondary endpoints will be analyzed with MMRM models; further details will be provided in the SAP:

- Changes from baseline in average instantaneous and reflective AM and PM CSNS and symptom scores (facial pain or pressure sensation, nasal discharge, and nasal congestion)
- Change from baseline SNOT-22 total scores and sub-domain scores
- Change from baseline to Week 24/ET in SNOT-22 total score in subjects from pooling studies OPN-FLU-CS-3205 and OPN-FLU-CS-3206 who report using an intranasal, topically acting nasal steroid for the treatment of CRS within 30 days of Visit 1
- Change from baseline PSQI global and component scores
- Change from baseline to Week 24/ET the Global PSQI Score from pooling studies OPN-FLU-CS-3205 and OPN-FLU-CS-3206
- Change from baseline to Week 4, 8, 12, and 24/ET in HPQ endpoints
  - number and percentage of missing work days over the past 4 weeks
  - percentage of productive work hours lost over the past 4 weeks

The following secondary endpoints will be analyzed using an ANCOVA model; further details will be provided in the SAP. Change from baseline to Week 24/ET:

- Lund-Mackay Staging System total score, scores for ethmoids and maxillary sinuses combined, and scores for each sinus pair (e.g., ethmoids, maxillary, frontal, sphenoid, and ostiomeatal complex),
- WPOV-E, WPOV-M, WPOV

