- Zinreich modification of the Lund-Mackay Staging System total score, scores for ethmoids and maxillary sinuses combined, and for each sinus pair (e.g., ethmoids, maxillary, frontal, and sphenoid)
- Zinreich modification of the Lund-Mackay Staging System score for the worst sinus between maxillary and ethmoid sinuses
- SF36v2 MCS Domain, PCS Domain, and individual health domains
- QIDS total score
- SIT scores

Change from baseline to Week 24/ET for EQ-5D VAS scores will be analyzed with the ANCOVA model described above; EQ-5D dimensions will be summarized. Further details will be provided in the SAP.

The percent of subjects considered improved (ie, subjects with ratings of 1 [very much improved] or 2 [much improved]) based on the PGIC at weeks 4 and 24/ET will be analyzed with a logistic regression MMRM model; further details will be provided in the SAP.

The Kaplan-Meier method and log-rank test will be used to estimate and compare the distributions of time to first exacerbation between OPN-375 and placebo.

The following endpoints will be analyzed using a logistic regression model; further details will be provided in the SAP:

- QIDS Severity of Depression at Week 24/ET
- The percent of subjects requiring rescue medication from Week 4 to Week 12; subjects without use of any rescue medication during the period Week 4 to Week 12 will be referred to as rescue-free subjects.
- The percentage of subjects who meet the eligibility criteria for surgery at Week 24

The percent of subjects indicating that they are willing to consider sinus surgery at baseline and Week 24, and the percent of subjects approved for surgery who no longer elect to undergo a surgery Week 24 within each treatment group will be compared with McNemar's test.

The total number of times a subject requires rescue medication after Week 4 to Week 12 will be tabulated. Rescue free subjects will be assigned a zero ('0') for this tabulation. This endpoint will be analyzed with an ANCOVA model based on ranks.

Change from baseline to Week 24/ET for SF-6D will be summarized as described in the SAP.

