7.1.2 Intercurrent Events

The potential intercurrent events are as follows:

1. Need for systemic corticosteroids for CRS exacerbation or worsening of CRS nasal/sinus symptoms
2. Need for nasal surgery; i.e., study discontinuation for nasal surgery
3. Discontinuation from study treatment

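### SAP 7.6.1 assigns no outcome to a subject who has nasal surgery on study, so the surgery-eligibility endpoint can leave that subject out or count the subject as improved

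*SAP*

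**What the plan says.** SAP 7.6.1 states that "The surgical intervention assessment (SIA) is performed at baseline and Week 24/ET". A subject is eligible for surgery if all four items for the baseline polyp stratum are met: "used a topical intranasal corticosteroid (≥ 8 weeks duration"); a course of systemic steroid (polyps) or antibiotic (no polyps); a SNOT-22 total of at least 20; and a Lund-Mackay score of at least 1.

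Two analyses follow. McNemar's test within each arm looks at how far "subjects improve ('Yes' at baseline to 'No' at Week 24/ET") as against the reverse. A logistic model compares arms at Week 24/ET with baseline eligibility as a covariate. For the analysis set, the section says: "Only subjects who have SIA completed at both baseline and Week 24/ET will be included in the analysis". It does not mention a subject who is operated on during the study.

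The general rules lie elsewhere:

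- Protocol 9.6 lists "The percentage of subjects who meet the eligibility criteria for surgery at Week 24" among its secondary analyses. The same section says: "Intercurrent events for secondary endpoints will be addressed as described in Section 9.3.3 for the primary estimand, unless otherwise indicated". It leaves the poor scores for the SAP to define.
- SAP 7.1.2 names as an intercurrent event "Need for nasal surgery; i.e., study discontinuation for nasal surgery". SAP 7.1.3 and Protocol 9.3.3 handle it by a composite strategy with a poor score, and do the same for systemic corticosteroids given for CRS.
- Other endpoints have their poor category written out: PGIC is set to not improved (SAP 7.5.8), SIT to 10 (SAP 7.5.11) and the EQ-5D VAS to 0 (SAP 7.6.2).

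**The concern.** The endpoint is meant to show whether treatment reduces the need for sinus surgery. A subject who has the operation is the plainest case of that need, yet SAP 7.6.1 does not say how to score one. Depending on when the last assessment falls, the same clinical course can lead to exclusion, 'eligible' or 'improved'. The last two point in opposite directions.

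Leaving operated subjects out, or scoring them 'not eligible', flatters whichever arm has more operations. Two programmers working from the present text could also produce different tables. The protocol appears to have settled the matter through its default, but the SAP supplies no category with which to carry that default out.

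**Working it through.** The documents give no surgery rate, eligibility rate or power for this endpoint, so there is no stated figure to reproduce. The check has two parts.

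**1. What the text does with an operated subject who was 'Yes' at baseline**

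| Week 24/ET assessment | Result under SAP 7.6.1 |
|---|---|
| Not done | Excluded by the both-visits rule |
| Done before the operation | 'Yes' if all four items are met |
| Done after the operation, SNOT-22 below 20 | 'No', counted as improved |

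All three paths are open. Protocol 6.5 asks early withdrawers to return for the early-termination visit, and the schedule puts this assessment at Week 24/ET, so exclusion follows only if that assessment is missing. The SAP describes leaving the study for surgery, so the last assessment may come before the operation.

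The third path usually runs through SNOT-22. Inclusion criterion 6 requires subjects to "have at least 1 sinus on each side of nose with a Lund-Mackay score of" 1 or more, so the baseline Lund-Mackay total is at least 1 + 1 = 2. To miss the threshold of 1 at Week 24, the total would have to reach 0.

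Under the primary-estimand default, all three rows would receive the poor category, 'eligible'.

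**2. How much the handling could matter**

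Inputs: n = 111 per arm (Protocol 9.1). Assumed: k operations in an arm, and a proportion p eligible among the other n − k subjects.

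- Operated subjects excluded: rate = p
- Scored 'not eligible': rate = p(n − k)/n
- Composite, scored 'eligible': rate = [p(n − k) + k]/n

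With p = 0.40 and k = 5, p(n − k) = 0.40 × 106 = 42.4:

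- excluded: 40.0%
- 'not eligible': 42.4/111 = 38.2%
- composite: (42.4 + 5)/111 = 42.7%

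Moving one subject between 'not eligible' and 'eligible' shifts the arm's rate by 1/111 = 0.9 points; five subjects shift it by 5/111 = 4.5 points. Excluding five instead of using the composite shifts it by 2.7 points.

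For the comparison between arms only the imbalance matters. The crude odds ratio of eligibility, active to placebo, is OR = [a/(1 − a)] / [b/(1 − b)], with a and b the two rates. Operations are assumed at 0 active and 2 placebo up to 3 active and 9 placebo:

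| Assumed p, active / placebo | Excluded | Composite | Scored 'not eligible' |
|---|---|---|---|
| 30% / 40% | 0.643 | 0.615 to 0.575 | 0.663 to 0.709 |
| 35% / 35% | 1.000 | 0.950 to 0.862 | 1.028 to 1.089 |

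Worked case, first row with 3 and 9 operations, composite: a = (0.30 × 108 + 3)/111 = 35.4/111 = 0.319; b = (0.40 × 102 + 9)/111 = 49.8/111 = 0.449; OR = 0.575. Scored 'not eligible': a = 32.4/111 = 0.292, b = 40.8/111 = 0.368, OR = 0.709.

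If operations are more frequent on placebo, the present handling understates a benefit. If they are more frequent on active, it does the reverse.

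**The case against.** The strongest reply is that the endpoint is defined without regard to actual operations. Protocol 2.3 and 7.3 and SAP 3.3.3 and 3.4.5 all say that the criteria are judged independently of any surgery performed, so forcing operated subjects to 'eligible' could be called a different endpoint. This wording is real and any fix has to be reconciled with it. Its most natural meaning, though, is that a subject can meet the criteria without being operated on. It does not justify reading a low SNOT-22 after an operation as a reduced need for surgery.

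The second reply is that the protocol default yields where something else is indicated, that the both-visits sentence may be that indication, and that the default in the SAP heads Section 7.5 while this endpoint is in 7.6. The SAP also uses a both-visits rule for the depression categories in 7.5.9. This stands so far as to rule out calling the matter a flat contradiction of the protocol. But 7.5.9 says outright that nothing is imputed, and SAP 7.6.2, in the same health-economic section, applies the composite to the EQ-5D VAS. A both-visits rule deals with absent assessments; it does not say how to score an assessment made after an operation. SAP 11 lists no change for this endpoint.

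The third reply is that the effect is small. Planned sinonasal surgery is an exclusion criterion, the endpoint lies outside the testing hierarchy in SAP 7.4, and SAP 7 gives nominal p-values outside it. All of that stands.

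**Conclusion.** SAP 7.6.1 lacks a rule that the protocol's default calls for. An operated subject may be excluded, remain 'eligible' or be counted as improved, according to the timing and presence of one assessment. The section neither implements the composite nor waives it.

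The likely size is small: at most 0.9 percentage points of an arm per operated subject. The operation counts and eligibility rates used above are assumptions. The conclusion also rests on the documents to hand: SAP 7.1.4 refers to an addendum of poor scores that is not among them. Its method, a percentile of change scores, would not fit a Yes/No endpoint.

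Four stronger readings are tempting and not supported:

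- That operated subjects are always dropped. An early-termination assessment is scheduled, so exclusion is conditional.
- That the gap manufactures a false benefit. The direction depends on which arm has more operations, which is unknown.
- That only SNOT-22 can move a subject to 'No'. Inclusion criterion 6 fixes Lund-Mackay at baseline only.
- That study drug, being an intranasal steroid, pushes active subjects towards 'eligible' through the treatment-history items, so those items should be frozen at baseline. Nothing says study drug counts, and a blinded site would count it in every arm or none. Freezing the items would also erase real escalation of treatment during the study.

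**What to change.** In SAP 7.6.1:

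1. State that the primary-estimand composite applies to the eligibility endpoint. A subject with nasal surgery before Week 24/ET is set to 'eligible = Yes' at Week 24/ET in both the McNemar table and the logistic model, including when the Week 24/ET assessment is missing.
2. Handle systemic corticosteroids given for CRS by the same default, or say explicitly that they are exempt and why. These subjects can reach Week 24 with an assessment, since Protocol 4.3 does not list such use as a reason for withdrawal.
3. Reconcile this with the wording in Protocol 2.3 and 7.3 and SAP 3.3.3 and 3.4.5, by saying that meeting the criteria does not require an operation but that an operation on study is assigned the poor category.
4. Keep the as-observed, both-visits analysis as a sensitivity analysis, and report the number of operated subjects per arm.

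The cost is a few lines of SAP text and one derivation rule, with no new data. The endpoint becomes a composite, and the proportion 'not eligible' may be slightly lower than under the present text.
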